5.6.3.6 Secondary Effectiveness Endpoint #6

The statistical analysis of secondary effectiveness endpoint #6 will consist of an estimate of the proportion of patients with freedom from Atrial Fibrillation, Atrial Tachycardia, Atrial Flutter regardless of AAD, defined as no documented event >30 seconds in duration (or for the entire length of a 30 second ECG tracing) regardless of AAD usage. This endpoint will be measured through the 12-month, 2, 3, 4, and 5-year visits (Visits 11-15 via cumulative 24-hour ECG monitor). The mITT, ITT and PP populations will be used for this analysis. Missing observations will be excluded.

Statistical Analysis Plan		Page 17 of 22
Sponsor	Study	Version
AtriCure	DEEP Pivotal Study	Version 2.0

The proportion will be calculated with subjects as the experimental unit. The numerator of the proportion will be the number of subjects with freedom from the aforementioned events and the denominator will be the total number of subjects without a missing observation. The endpoint will be presented through each visit for each analysis population with the numerator and denominator, the proportion and its 95% two-sided exact binomial confidence interval. A similar summary will be provided for each yearly visit; if a subject fails at a given year they will be counted as a failure for subsequent yearly visits.

5.6.3.7 Secondary Effectiveness Endpoint #7

The statistical analysis of secondary effectiveness endpoint #7 will consist of an estimate of the proportion of patients with freedom from any documented AF, atrial flutter, or atrial tachycardia lasting >10 minutes in duration through the 12-month follow-up visit in the absence of Class I or III AADs (with the exception of previously failed AADs at doses not exceeding those previously failed). The mITT, ITT and PP populations will be used for this analysis. Missing observations will be excluded.

The proportion will be calculated with subjects as the experimental unit. The numerator of the proportion will be the number of subjects with freedom from the aforementioned events and the denominator will be the total number of subjects without a missing observation. The endpoint will be presented for each analysis population with the numerator and denominator, the proportion and its 95% two-sided exact binomial confidence interval.

5.6.3.8 Secondary Effectiveness Endpoint #8

The statistical analysis of secondary effectiveness endpoint #8 will consist of an estimate of the change in Quality of Life, defined as the total AFEQT score measured at the 12-month follow-up visit minus the score at the baseline visit. The score will be calculated per the AFEQT scoring manual. The mITT, ITT and PP populations will be used for this analysis. Missing observations will be excluded.

The difference in scores will be calculated with subjects as the experimental unit. The mean difference of AFEQT scores will be presented for each analysis population with its 95% confidence interval using the t-distribution. The standard deviation, median, minimum, maximum, and number of evaluable observations will also be presented.

5.6.4 Secondary Safety Endpoints

All secondary safety endpoints are supplemental and intended to provide a more complete picture of the overall safety profile for the DEEP procedure. They will not be tested for labeling purposes. Analysis of secondary safety endpoints will be based on descriptive statistics and nominal two-sided 95% confidence intervals for observed data, with methods as described in section 5.1.1. All secondary safety endpoints will be presented as exploratory analyses; no statistical inference will be performed.

Statistical Analysis Plan		Page 18 of 22
Sponsor	Study	Version
AtriCure	DEEP Pivotal Study	Version 2.0

5.6.4.1 Secondary Safety Endpoint #1

The statistical analysis of secondary safety endpoint #1 will consist of an estimate of the proportion of patients with a major surgical event. This will be a composite safety endpoint within 30 days of the epicardial surgical procedure, as otherwise defined in the primary safety endpoint events described in section 2.1.2. The safety population will be used for this analysis. Missing observations will be excluded.

The proportion will be calculated with subjects as the experimental unit. The numerator of the proportion will be the number of subjects with a major surgical event and the denominator will be the total number of subjects without a missing observation. The endpoint will be presented with the numerator and denominator, the proportion and its 95% two-sided exact binomial confidence interval.

5.6.4.2 Secondary Safety Endpoint #2

The statistical analysis of secondary safety endpoint #2 will consist of an estimate of the proportion of patients with a major catheter event. This will be a composite safety endpoint within 7 days of the endocardial catheter procedure, as otherwise defined in the primary safety endpoint events described in section 2.1.2. The safety population will be used for this analysis. Missing observations will be excluded.

The proportion will be calculated with subjects as the experimental unit. The numerator of the proportion will be the number of subjects with a major catheter event and the denominator will be the total number of subjects without a missing observation. The endpoint will be presented with the numerator and denominator, the proportion and its 95% two-sided exact binomial confidence interval.

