4.2.2 Enrollment

Patients are considered **enrolled** in the study when they have signed an informed consent. Subjects are considered **treated** upon induction of anesthesia during the Epicardial Surgical Ablation Procedure.

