4.4 Follow-up for Early Terminated Subjects

Given the nature of the study procedures, there are situations where subjects may terminate from the study early that are not described above. The required subject follow-up, depending on the study procedures completed, is as follows:

- If an enrolled subject is found to not meet the study eligibility criteria, or withdraws consent before the induction of anesthesia, the subject will exit the study (complete study exit page) without study follow-up.
- If a subject is enrolled and undergoes anesthesia (treated) (e.g., clot is detected in LA or LAA), the subject will complete a limited discharge study visit and the 30-day assessment and then will exit the study (complete study exit page). The procedures required for the limited discharge and 30-day Visit are:
 - Targeted Physical Examination
 - Medication Review
 - Adverse Event Assessment
 - Discharge Date (for hospital discharge only)

If a subject is enrolled and is treated and is **converted to a sternotomy or thoracotomy** during the Epicardial Surgical Ablation Procedure, the subject will be followed through the 12 Month visit. After the 12-month follow up visit, the subject will exit the study (complete study exit page) without additional study follow-up.

If a subject is treated with the Epicardial Surgical Ablation Procedure, and withdraws before the Endocardial Ablation Procedure, the subject will be followed for at least to the 1-Month Visit after the Epicardial Procedure to follow for safety. After the 1-Month follow up visit, the subject will exit the study (complete study exit page) without additional study follow-up.

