7.2 Visit 2 – Epicardial Surgical Ablation Procedure

NOTE: At the time of scheduling the subject's Epicardial Surgical Ablation Procedure, sites are encouraged to schedule the subject's Endocardial EP Ablation Procedure, for 91-121 days following surgery. Scheduling the Endocardial EP Ablation Procedure at the time of the subject's surgical procedure will ensure the subject's EP procedure occurs within the protocol visit window.

The Epicardial Surgical Ablation Procedure (**See Section 5.1**) will be performed within 45 days of the subject consenting to the clinical study. If the Epicardial Surgical Procedure is delayed, the subject must be re-consented and baseline tests repeated if necessary, for protocol defined windows.

The following must be conducted and/or obtained prior to or during the Epicardial Surgical Ablation Procedure:

- Confirm Inclusion/Exclusion criteria
- Esophagoscopy
- Note: Esophagoscopy to be performed prior to the placement of access ports for the epicardial procedure.
- Transesophageal Echo (TEE) – (performed at the beginning of the surgical procedure prior to placement of access ports, to confirm study eligibility and rule out thrombus in the left atrium or LAA. If a thrombus is present in the left atrium or LAA on TEE, the subject should not have the surgical ablation procedure performed.)

- Surgical Procedure Details (including procedure times)
- Surgical Ablation Details (including ablation and lesion details)
- LAA Management Details
- TEE Assessment (following exclusion of LAA)
- Adverse Event Assessment
- Post procedure Heart Rhythm Assessment – 30 second ECG
- Medications Review: Anticoagulation/antiplatelet therapy administered during surgical intra-procedure

Note: If patient requires conversion to either a thoracotomy or sternotomy during the surgical ablation procedure, they should not receive the catheter ablation procedure, and will be followed for 12 months.

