5.2 Analysis Populations

Intent to treat patient population (ITT): The ITT subject population will include all subjects who have met all inclusion/exclusion criteria and on whom a procedure was attempted (defined as a subject who underwent induction of anesthesia).

Modified intent to treat patient population (mITT): The mITT subject population will include all subjects who attempted the Epicardial Procedure (defined as a subject who underwent induction of anesthesia) and have at least one post-procedure follow-up visit after the 2nd Blanking Period (with the 2nd blanking period defined as the 90-days post Endocardial Ablation Procedure) with non-missing primary effectiveness data.

Safety Population: The safety population will include all enrolled subjects that undergo induction of anesthesia.

Per protocol patient population (PP): The PP patient population will include all subjects who complete both the Epicardial Surgical Ablation Procedure and Endocardial EP Ablation Procedure.

AtriClip Effectiveness population: The AtriClip effectiveness population will include all ITT subjects for whom an attempt (entrance of the AtriClip into the chest wall) is made to place an AtriClip device.

The primary effectiveness analysis will utilize the mITT patient population as defined in this statistical analysis plan. The analysis will be repeated on the ITT and PP patient populations as supportive analyses. Secondary effectiveness analyses will be conducted on the mITT, the ITT and the PP patient populations. All safety analyses will utilize the safety population.

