5.3 Handling of Missing Data

All safety analysis will utilize the safety population and no missing values will be imputed unless a subject misses a follow-up visit and cannot subsequently be contacted to determine their primary safety status. In this case, the primary safety endpoint will be considered a failure and the subject will be excluded from any subsequent secondary safety analyses for which their status is unknown. If a procedure is aborted due to a primary safety event, the subject will be considered a safety failure. If a subject misses a follow up visit, but it can be subsequently verified that the subject did not incur a safety failure, the subject will be considered a success. As an additional analysis, the primary safety endpoint will be analyzed based on only observed failures, with all other subjects in the Safety Population counting as a success.

The primary effectiveness analysis will utilize the mITT population and the LOCF method for missing values, as defined below. A subject with any primary effectiveness failure from the 6-month visit

Statistical Analysis Plan		Page 12 of 22
Sponsor	Study	Version
AtriCure	DEEP Pivotal Study	Version 2.0

through the 12-month visit will be considered a failure for all methods below. Any subjects who withdraw or are lost-to-follow-up after the 6-months visit (post AAD optimization) but prior to the 12-month follow-up visit, or for any reason do not have 12-month ECG readings available, will be analyzed as follows:

- 1) Last observation carried forward (LOCF): Any subject who is missing a scheduled testing will be considered an effectiveness success or failure at that scheduled visit based on their status up to and including their last testing.
- 2) Worst case: Any subject with no primary effectiveness failure recorded and with no 12-month test data will be considered a failure.
- 3) Best case: Any subject with no primary effectiveness failure recorded and with no 12-month test data will be considered a success.
- 4) Break-even: If the study endpoint is met using the best-case methodology and is not met using the worst-case methodology, a break-even analysis will be performed to determine the number of subjects with missing endpoint data who would be required to be a success in order to meet the endpoint.

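### The denominator for major catheter events is not limited to subjects who had a catheter procedure, so the catheter-stage rate may be diluted

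*SAP*

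**What the plan says.** SAP 5.6.4.2 (Secondary Safety Endpoint #2) ties the event to the catheter stage: "This will be a composite safety endpoint within 7 days of the endocardial catheter procedure". It then names the population and the missing-data rule: "The safety population will be used for this analysis. Missing observations will be excluded". The proportion is formed so that "the denominator will be the total number of subjects without a missing observation".

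SAP 5.2 defines the population: "The safety population will include all enrolled subjects that undergo induction of anesthesia". Protocol 4.2.2 makes clear which anesthesia marks a subject as treated: "upon induction of anesthesia during the Epicardial Surgical Ablation Procedure". Membership therefore does not depend on reaching the endocardial procedure.

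The protocol foresees treated subjects who do not reach it:

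- **Conversion to sternotomy or thoracotomy.** Protocol 7.2 says "they should not receive the catheter ablation procedure, and will be followed for 12 months".
- **Withdrawal before stage 2.** Protocol 4.4 says that if a subject "withdraws before the Endocardial Ablation Procedure, the subject will be followed for at least to the 1-Month Visit"; the subject then exits.
- **Surgery not carried out after anesthesia**, for example because of thrombus. Under Protocol 4.4 the subject has a 30-day assessment and exits.
- **Refusal of stage 2, or an event or condition that precludes it.** Protocol 9.2.1 asks sites to keep collecting follow-up to 12 months after surgery.

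The closest general rule on leaving a secondary safety analysis is in SAP 5.3. After a missed visit and failed contact, "the subject will be excluded from any subsequent secondary safety analyses for which their status is unknown".

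**The concern.** A subject who never had an endocardial procedure has no 7-day window after one and cannot contribute an event. If that subject stays in the denominator, the proportion no longer estimates the risk of the catheter stage among those exposed to it. It estimates the product of that risk and the chance of reaching stage 2. The error can only run toward a lower, more favourable catheter rate.

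The SAP does not say how such subjects are classed. Two programmers could follow 5.6.4.2 in good faith and report different rates from the same data. The denominator wording is the same as in 5.6.4.1, where it suits the surgical endpoint because everyone in the safety population has entered the surgical stage.

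**Working it through.** The documents state no expected rate, sample size or precision for this endpoint, so there is no figure to reproduce. The check has two parts.

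**1. Who stays in the denominator as the SAP is written?**

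| Subject without a catheter procedure | Follow-up in the protocol | Status under SAP 5.3 and 5.6.4.2 |
|---|---|---|
| Converted to sternotomy or thoracotomy | To 12 months (4.4, 7.2) | Known: no catheter procedure, no catheter event. Not clearly missing |
| Refuses or is precluded from stage 2 | 12-month data sought (9.2.1) | Known where follow-up succeeds. Not clearly missing |
| Withdraws before stage 2 | At least to 1 month, then exits (4.4) | Usually gone before the Day 91–121 window; may drop out as missing |
| Surgery not carried out after anesthesia | 30-day assessment, then exits (4.4) | Usually gone before that window; may drop out as missing |

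SAP 5.3 links exclusion to unknown status. The status of the first two groups is known, so that rule does not clearly remove them. SAP 5.6.3.4 gives modest support: it analyses acute success of the endocardial procedure in both the ITT and PP populations with missing observations excluded. If having no catheter procedure always meant missing, those two analyses would be largely redundant.

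**2. How large is the effect if they are counted as event-free?**

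Let n_c be the number catheterised, n_k the number never catheterised but kept in the denominator, and r the rate among the catheterised.

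Reported rate = r × n_c / (n_c + n_k) = r × (1 − f), where f = n_k / (n_c + n_k). The relative understatement is f.

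Inputs:

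- Treated subjects: 220, the planned maximum (Protocol 9.3).
- f = 4%: in the staged feasibility study 25 subjects had surgery and 24 had the endocardial procedure (Protocol 1.0), so 1/25 = 4%.
- f = 20%: assumed upper bound. Protocol 9.3 allows about 20% attrition, but that covers loss up to the 12-month effectiveness endpoint, not failure to reach stage 2.
- f = 10%: an intermediate assumption.
- Subjects with an event: 10, purely illustrative.
- All never-catheterised subjects are kept as event-free. This is the least favourable case for the current wording.

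| f | Catheterised | All-treated rate (95% exact CI) | Rate among catheterised (95% exact CI) | Difference |
|---|---|---|---|---|
| 4% | 211 | 10/220 = 4.55% (2.20–8.20) | 10/211 = 4.74% (2.30–8.54) | 0.2 points |
| 10% | 198 | 10/220 = 4.55% (2.20–8.20) | 10/198 = 5.05% (2.45–9.09) | 0.5 points |
| 20% | 176 | 10/220 = 4.55% (2.20–8.20) | 10/176 = 5.68% (2.76–10.20) | 1.1 points |

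The reported rate is 0.96, 0.90 and 0.80 times the rate among catheterised subjects. If never-catheterised subjects are instead excluded as missing, n_k = 0 and there is no dilution.

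**The case against.** A reader might infer that the SAP divides catheter events by the whole safety population, so that the rate falls in proportion to all stage-2 dropout. The documents do not support that. The denominator sentence removes missing observations, SAP 5.3 leaves a subject with a missing secondary value out of that analysis, and SAP 5.6.4 speaks of observed data. A subject with no catheter procedure has no post-catheter window to observe, so calling that observation missing is a defensible reading, and it gives no dilution. Subjects who withdraw early or whose surgery is not carried out usually exit before Day 91, so the group at issue is smaller than total stage-2 dropout.

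An all-treated denominator is also legitimate. SAP 5.6.4 says these endpoints describe the safety of the DEEP procedure overall, and the primary safety composite uses the same base. The consequences are limited: the endpoint is descriptive, it is outside the success criterion in SAP 5.6, and the numerator and denominator will both be shown. SAP 5.4 also tabulates completion by visit, so a reader could largely reconstruct the exposed rate.

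Most of this stands, and it limits the point to an unspecified denominator with a possible, modest dilution. It does not settle how converted subjects, or subjects followed without stage 2, are counted. Nor does 5.6.4.2 present its proportion as a whole-strategy rate; it describes patients with a major catheter event, and the primary composite already covers both stages.

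**Conclusion.** The point holds as a minor one. SAP 5.6.4.2 applies a population defined at the surgical stage to an endpoint that exists only after the catheter stage, and it does not restrict the denominator to subjects exposed to that stage. Subjects with known follow-up but no endocardial procedure would most naturally count as event-free. The catheter rate is then understated by their share of the denominator.

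That share is about 4% relative if the feasibility figure carries over. It rests on one subject in 25, in a study with 1–10 days between stages rather than 91–121, so it is a weak guide. The 20% figure is only an assumed ceiling. With 10 events among 220 treated subjects, the range is 0.2 to 1.1 percentage points, and it is zero if these subjects are treated as missing. Dilution is therefore possible and the likelier reading, but not established. No hypothesis test or success decision is affected.

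**What to change.** In SAP 5.6.4.2, define the denominator as safety-population subjects in whom at least one endocardial ablation procedure was started. State that subjects who never had one are outside this denominator, report their number, ideally by reason, and show the all-treated proportion alongside as the whole-strategy figure.

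Procedure started is a better criterion than the PP population, which requires completion of both procedures and could drop a subject whose catheter procedure was stopped because of a complication. SAP 5.2 already has an exposure-based set of this kind: the AtriClip population is defined by attempted placement.

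The cost is one SAP sentence and a slightly less favourable catheter rate. No new data are needed.

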5.6.4.3 Secondary Safety Endpoint #3

The statistical analysis of secondary safety endpoint #3 will consist of an estimate of the proportion of patients with a surgical SAEs within 30 days of surgery. This will include all SAEs that occur within 30 days of the epicardial surgical procedure and that are adjudicated to be related to the device or to the procedure. The safety population will be used for this analysis. Missing observations will be excluded.

The proportion will be calculated with subjects as the experimental unit. The numerator of the proportion will be the number of subjects with a surgical SAE and the denominator will be the total number of subjects without a missing observation. The endpoint will be presented with the numerator and denominator, the proportion and its 95% two-sided exact binomial confidence interval.

5.6.4.4 Secondary Safety Endpoint #4

The statistical analysis of secondary safety endpoint #4 will consist of an estimate of the proportion of patients with DEEP SAEs within 12-months. This will include all SAEs through the 12-month follow-up visit that are adjudicated to be related to an AtriCure device or to either stage of the DEEP procedure. The safety population will be used for this analysis. Missing observations will be excluded.

Statistical Analysis Plan		Page 19 of 22
Sponsor	Study	Version
AtriCure	DEEP Pivotal Study	Version 2.0

The proportion will be calculated with subjects as the experimental unit. The numerator of the proportion will be the number of subjects with a DEEP related SAE and the denominator will be the total number of subjects without a missing observation. The endpoint will be presented with the numerator and denominator, the proportion and its 95% two-sided exact binomial confidence interval.

5.6.4.5 Secondary Safety Endpoint #5

The statistical analysis of secondary safety endpoint #5 will consist of an estimate of the proportion of patients with an unresolved SAE. This will include all SAEs through the 12-month follow-up visit that are adjudicated to be related to an AtriCure device or to either stage of the DEEP procedure and that are not fully resolved by the 12-months visit. These events shall include any procedure-related deaths, strokes with residual disability, unresolved phrenic nerve damage, or other such events that are adjudicated to have resulted in chronic disability or permanent damage. The safety population will be used for this analysis. Missing observations will be excluded.

The proportion will be calculated with subjects as the experimental unit. The numerator of the proportion will be the number of subjects with an unresolved SAE and the denominator will be the total number of subjects without a missing observation. The endpoint will be presented with the numerator and denominator, the proportion and its 95% two-sided exact binomial confidence interval.

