Patients with persistent AF are at increased risk of ischemic stroke and heart failure, while they may also be at increased risk of hemorrhagic stroke due to oral anticoagulation. In addition, their quality of life and ability of work can be greatly affected by both the disease and by the medications

used to treat the disease. All of the patients in this study will have tried and failed at least one treatment and many have failed several treatments, whether multiple AADs or AADs and catheter ablation.

The patients themselves and their treating physicians are willing to tolerate a substantial level of risk, if the reward is a similarly substantial level of benefit. The tolerable risk level, from the perspective of both the patients and the treating physicians, is related more to the subset of events that would cause permanent damage (i.e., death, stroke, MI, permanent and significant phrenic nerve damage) than to the overall level of procedure-related SAEs. It is believed that the rate of this subset of events will be quite low in the proposed study and that the benefit to the patient in terms of AF reduction or resolution, substantially reduced stroke risk, heart failure risk, and bleeding risk, and a substantial increase in quality of life will be the expected benefits.

There have been no regulated trials in this persistent AF population for a treatment that has produced the magnitude of benefit expected in this trial, and thus there is no comparable published standard for acceptable risk in relation to benefit. Rather, the acceptable risk level is proportionate to a patient's current risk profile and quality of life, based on their AF, and the anticipated level of benefit from the proposed treatment.

For these reasons, the clinicians involved in this study have agreed that a 28% rate of safety events, as specifically defined in the primary safety endpoint, and with the expected mix of permanent vs. resolvable events, is an acceptable risk level in relation to the expected benefits of this treatment.

In order to have an 80% chance of showing that the DEEP procedure has a primary safety event rate of <28% (UCL) when the actual underlying rate is 19%, a sample size of N=192 subjects is required. This sample size calculation is based on a one-sided $\alpha=0.025$ level of significance and assumes a normal approximation to the binomial distribution with continuity correction.

Overall Sample Size

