All secondary endpoints for LAA exclusion will utilize the LOCF method for missing values. No missing values will be imputed for the remaining secondary endpoints. If a subject is missing a value for one of these secondary endpoints, they will not be included in the analysis of that endpoint. The number of patients with non-missing values will be reported for each endpoint.

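### The unresolved-SAE endpoint excludes subjects with unknown 12-month status and has no rule for a related SAE still ongoing at last contact, so an observed harm such as a phrenic nerve injury can drop out of the rate.

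*SAP*

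**What the plan says.** SAP 5.6.4.5 defines endpoint #5 through SAEs related to an AtriCure device or to either stage of the procedure "that are not fully resolved by the 12-months visit". It names events that must be included: procedure-related deaths, and "strokes with residual disability, unresolved phrenic nerve damage, or other such events that are adjudicated to have resulted in chronic disability or permanent damage". The missing-data rule is "The safety population will be used for this analysis. Missing observations will be excluded", and "the denominator will be the total number of subjects without a missing observation".

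SAP 5.3 covers the subject who misses a visit and cannot be reached to establish primary safety status. For the primary endpoint: "In this case, the primary safety endpoint will be considered a failure". For the secondary safety endpoints: "the subject will be excluded from any subsequent secondary safety analyses for which their status is unknown". For secondary endpoints other than LAA exclusion it adds: "If a subject is missing a value for one of these secondary endpoints, they will not be included in the analysis of that endpoint". Protocol 9.9 carries the same rules.

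Two other places matter. Item j of the primary composite (SAP 2.1.2) and Protocol Appendix 5 both tie permanence of phrenic nerve paralysis to 12 months. Protocol 10.3 requires the investigator to give the outcome of every adverse event.

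**The concern.** The endpoint depends on status at one late time, and the rule for not knowing that status is exclusion. A subject whose related SAE was recorded as ongoing at the last contact, and who then leaves or dies of another cause before Visit 11, has no 12-month status. The database nevertheless holds the event and its last outcome. Exclusion discards that information.

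Some of this missingness can be foreseen. Under Protocol 4.4, a subject who withdraws before the endocardial stage is followed at least to the 1-month visit and then exits. Under Protocol 10.5.2, follow-up of an unresolved SAE may end at study exit. Protocol 9.3 allows for about 20% attrition. Protocol 9.2.1 expects some subjects to miss the second stage because of a safety event, although it also says that follow-up will be attempted.

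The stake is interpretive. Protocol 9.3 defends the 28% safety limit by saying that the tolerable risk level "is related more to the subset of events that would cause permanent damage" than to all procedure-related SAEs, and expects those events to be rare. Endpoint #5 is the planned summary that pools lasting harm, so readers will set it beside that argument.

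**Working it through.** **Step 1: the passages side by side.** Consider a subject with a related SAE who has no Visit 11.

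| Situation | Primary safety (SAP 2.1.2, 5.3) | Endpoint #5 (SAP 5.6.4.5, 5.3) |
|---|---|---|
| Procedure-related death | Failure if within the window | Named for inclusion |
| Stroke already adjudicated as leaving residual or permanent disability | Known failure if within the 30-day or 7-day window | Named for inclusion |
| Phrenic paralysis ongoing when the subject is lost | Item j cannot be settled; scored as failure | 12-month status unknown; excluded |
| Other related SAE ongoing, not adjudicated as permanent | Depends on the event | Excluded, unless an ongoing outcome is read as an observation |

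The third row is the firm case and the fourth is open. No section says that an SAE ongoing at last contact counts as unresolved, and the term missing observation is not defined for this event-based endpoint.

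**Step 2: size under differential dropout.** The plan states no rate, sample size or power for endpoint #5, so there is no figure to reproduce. Let p be the true unresolved proportion, d1 the share of harmed subjects without 12-month status, and d0 the share of the others. Only subjects with known status enter the rate, so

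reported rate = p(1 − d1) / [p(1 − d1) + (1 − p)(1 − d0)].

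All values of p, d1 and d0 are assumptions.

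- p = 0.05, d1 = 0.40, d0 = 0.15: 0.0300 / (0.0300 + 0.8075) = 3.6%. With 220 treated, 11 are harmed and 4.4 of them are dropped.
- p = 0.10, same dropout: 0.060 / (0.060 + 0.765) = 7.3%.
- d1 = 0.50, d0 = 0.15: 0.0250 / 0.8325 = 3.0% for p = 0.05, and 0.050 / 0.815 = 6.1% for p = 0.10.
- d1 = d0: the factor cancels and the reported rate equals p.

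The formula applies d1 to every harmed subject. Procedure-related deaths and adjudicated permanent events cannot be lost this way, so p here means the events that can be.

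**Step 3: size in counts.** Assume 220 in the safety population, 44 (20%) without 12-month status, 5 unresolved SAEs among the 176 with known status, and 3 of the 44 with a related SAE ongoing at last contact. Intervals are Clopper-Pearson 95%.

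- As written: 5/176 = 2.8% (0.9 to 6.5).
- Ongoing cases counted, known status: 8/179 = 4.5% (2.0 to 8.6).
- Ongoing cases counted, full safety population: 8/220 = 3.6% (1.6 to 7.0).

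The scenarios run used 11, 22 or 44 lost, 2, 5 or 10 observed, and 1, 3 or 5 ongoing. Across them the gap between the first two rates runs from 0.45 points (10/209 = 4.78% against 11/210 = 5.24%) to 2.7 points (2/176 = 1.14% against 7/181 = 3.87%).

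**Step 4: the other direction.** Exclusion also removes event-free subjects. If none of the 44 had an ongoing event, the rule gives 5/176 = 2.8% against 5/220 = 2.3% over the full population. The net direction therefore depends on who leaves.

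**The case against.** The best defence is that an SAE recorded as ongoing is an observation, so a programmer could count it without breaking SAP 5.6.4.5. That reading is possible, but the SAP does not state it, and it is weakest for phrenic nerve injury because permanence has to be documented at 12 months or later. Two programmers could produce different rates from the same data.

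Several stronger readings are tempting, and the documents do not support them:

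- *A subject with a disabling stroke is dropped.* Not if the disability has been adjudicated, since SAP 5.6.4.5 names such strokes for inclusion.
- *The primary and secondary rules conflict for every such subject.* A related stroke that is an SAE within the window is already a known primary failure, so the unknown-status rule is not triggered. The contrast holds where primary status itself waits on 12 months, as in item j.
- *Endpoint #5 is the only measure of permanent harm.* The events listed in Protocol 9.3 (death, stroke, MI, permanent phrenic damage) are all primary components. Endpoint #4 counts related SAEs through 12 months whether or not they resolve, endpoint #7 covers stroke and TIA, and SAP 7 plans subject listings.
- *The rate is certainly biased downward.* The dropout split is assumed, and step 4 shows an upward effect. The protocol also works against loss of harmed subjects: SAEs are followed to resolution or exit (10.5.2), and final observations are sought at withdrawal (4.3).

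It is also fair to say that the endpoint is supplemental and not tested (SAP 5.6.4), which limits the consequence.

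**Conclusion.** The concern holds in a limited form. The exclusion of unknown 12-month status is a stated rule. Nothing protects a related SAE that was ongoing at last contact and has not been adjudicated as permanent or disabling. Phrenic nerve injury is the clear example: a lost subject is a failure in the primary safety analysis and can be absent from endpoint #5.

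The size cannot be fixed from the documents. On the assumptions shown, a true 5% is reported as 3.0% to 3.6% and a true 10% as 6.1% to 7.3%, with no bias when dropout is equal in harmed and other subjects. No hypothesis test or success criterion is affected. What is affected is how far the reported rate of lasting harm can be relied on next to the risk argument in Protocol 9.3. This is a correction worth making before analysis, and it does not threaten the primary conclusions.

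**What to change.** In SAP 5.6.4.5, replace the sentence on missing observations with:

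> A related SAE recorded as ongoing at last contact, exit or death before Visit 11 is counted as unresolved, and is not a missing observation. The rate is shown over the full safety population and over subjects with known status, with the number of subjects lacking 12-month status and no ongoing related SAE.

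Three consequential edits are needed. The denominator sentence in SAP 5.6.4.5 must match. SAP 5.3 must say that endpoint #5 is an exception both to its exclusion of unknown status and to its rule against imputation. The same exception must be recorded against Protocol 9.9. Without these the new sentence would contradict the general rules.

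Both denominators are needed because neither is neutral. The known-status rate keeps leavers with an ongoing event while omitting event-free leavers, so it leans high. The full-population rate assumes that leavers without an ongoing related SAE had none later.

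The change uses the outcome already collected under Protocol 10.3. Its cost is text in two documents, a slightly less favourable rate, and the counting of some events that would have resolved after the subject left, including a nerve palsy still present at a 1-month exit. It is an analysis rule and changes no clinical management.
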